Reason for change in	• 2nd dose: "a reason for other than 80mg (a dose) or in the case
dose/dosing frequency	of self-administration" in the survey form.
	• 3rd and the subsequent dose(s): "a reason for other than 40mg
	(a dose), or in the case of other than once every 2 weeks
	(dosing frequency)" or "reason for change in dose/dosing
	frequency" in the survey form.
	Dosing frequency
	[1] Sort data in the order of "the first administration date" of "the
	administration status of Humira", dosing frequency and
	description.
	[2] Calculate the dosing interval per data on administration status
	The interval between first and second administrations should
Administration status	be 14 days.
	• For the third and subsequent dose(s), the interval should be 14
(total number of dosing,	days if the dosing frequency "once every 2 weeks" is checked
total dose)	while the dosing frequency should be obtained from "[Humira
	UC] Conversion data provided for analysis" if the dosing
	frequency is "others".
	[3] Calculate the dosing frequency per data on administration
	status.
	Dosing frequency = (the final administration date (after
	imputed) – the first administration date(after imputed))/dosing

Data name	Derivation and calculation methods
	frequency (number of days)
	[4] When the results of [3] are ">0" (bigger than 0) and "<1"
	(smaller than 1), the dosing frequency shall be counted as 1.
	If the figure is ">=1" (1 or bigger), round the decimal down to the
	integer for the dosing frequency.
	[5] The total number of dosing shall be the total of [4] per patient.
	• Dose
	[1] If "Others" of a Humira dose is checked, the dose should be
	obtained from "[Humira UC] Conversion data provided for
	analysis".
	[2] Calculate the dose per data of the administration status.
	Dose = the number of dosing * a dose
	[3] The total dose should be the total of [2] per patient.
	• The mean daily dose
	The mean daily dose = the total dose/the total number of dosing
	If a patient's final administration date of Humira comes before the
	first administration date of Humira + 336, we handle the patient as a
Discontinued patients	discontinued case.
	Follow the above definition, no matter whether the discontinuation is
	selected in the survey form.
	"Present" is defined for the situation where a patient qualifies for the
	defined discontinued case and at least one has been checked in
Presence/absence of	"reason for discontinuation" of "discontinuation of the survey" of the

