	Not conducted: other than the above
Presence/absence of prior	The drug names described in "prior-medication history for colitis
medications	ulcerative" in the survey form should be regarded as the prior

Data name	Derivation and calculation methods
	medications. Note that when a drug code is null, it is not regarded as a prior medication. When prior-medication data are contained in the survey form, it
Presence/absence of prior medication (aminosalicylic acid	when prior-medication data are contained in the survey form, it should be classified as "with prior medication". When there is no description of "presence/absence of prior medications" in the survey form or the assessment is impossible, it should be classified as "unknown/not provided", and other cases are "without prior medications". Refer to "171218 drug list_UC". If prior-medication data of the applicable drug code are provided in the survey form, or if an aminosalicylic acid drug in the survey form is checked, regard the case as "with aminosalicylic acid". Others are "without
drug)	aminosalicylic acid". Refer to "171218 drug list UC". If prior-medication data of the
Presence/absence of prior medication (corticosteroids)	applicable drug code are provided in the survey form, or if corticosteroids in the survey form is checked, regard the case as "with corticosteroids". Others are "without corticosteroids".
Presence/absence of prior medication (azathioprine)	Refer to "171218 drug list_UC". If prior-medication data of the applicable drug code are provided in the survey form, or if azathioprine in the survey form is checked, regard the case as "with azathioprine". Others are "without azathioprine".
Presence/absence of prior medication (6-mercaptopurine)	Refer to "171218 drug list_UC". If prior-medication data of the applicable drug code are provided in the survey form, or if 6-mercaptopurine in the survey form is checked, regard the case as "with 6-mercaptopurine". Others are "without 6-mercaptopurine".
Presence/absence of prior medication (azathioprin & 6-mercaptopurine)	Refer to "171218 drug list_UC". If prior-medication data of the applicable drug code are provided in the survey form, or if azathioprin and 6-mercaptopurine in the survey form are checked, regard the case as "with azathioprin & 6-mercaptopurine". Others are "without azathioprin & 6-mercaptopurine".

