	(including surgery)" of the survey form, regard it as a prior treatment.
Dungan og/ohannon of	When prior-treatment data are contained in the survey form, it should
Presence/absence of prior treatment	be classified as "with prior treatment". When there is no description
	of "presence/absence of prior treatment" in the survey form or the
	assessment is impossible, it should be classified as "unknown/not
	provided", and other cases are "without prior treatment".
Draganaa/ahaanaa af	Surgery should be selected if the checkbox of prior treatment
Presence/absence of	(surgery) in "prior treatment for colitis ulcerative (including
prior treatment (surgery)	surgery)" is checked and if any prior treatment considered as surgery

Data name	Derivation and calculation methods
	is included in "[Humira UC] Conversion data provided for analysis".
	When the data applicable to surgery are contained, regard it as "with
	surgery". Others are "without surgery".
	If "leukocytapheresis" in "prior treatment (including surgery) for
Presence/absence of	colitis ulcerative" is checked and it is not applicable to with prior
prior treatment	treatment (surgery) in the survey form, it shall be classified into
(leukocytapheresis)	"with leukocytapheresis". Other cases are "without
	leukocytapheresis".
	If "enteral nutrition therapy" in "prior treatment (including surgery)
Presence/absence of	for colitis ulcerative" is checked and it is not applicable to with prior
prior treatment (enteral	treatment (surgery) in the survey form, it shall be classified into
nutrition therapy)	"with enteral nutrition therapy". Other cases are "without enteral
	nutrition therapy".
Presence/absence of	If "intravenous nutrition therapy" in "prior treatment (including
	surgery) for colitis ulcerative" is checked and it is not applicable to
prior treatment	with prior treatment (surgery) in the survey form, it shall be classified
(intravenous nutrition	into "with intravenous nutrition therapy". Other cases are "without
therapy)	intravenous nutrition therapy".
Presence/absence of	If "other therapy" in "prior treatment (including surgery) for colitis
	ulcerative" is checked and it is not applicable to with prior treatment
prior treatment (other	(surgery) in the survey form, it shall be classified into "with other
therapy)	therapy". Other cases are "without other therapy".
	Concomitant medications should the data satisfying the following
	rules: Note that when a drug code is null, it is not regarded as a

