	concomitant-therapy data are contained in the survey form, it should
	be classified as "with concomitant therapy". When "presence/absence
	of prior/concomitant medications" is not provided in the survey form
	or the assessment is impossible, it should be classified as
	"unknown/not provided", and other cases are "without concomitant
	therapy".
	Surgery should be selected when the 'surgery' checkbox of
	non-medicinal treatment/concomitant therapy name is checked in
D /1 C	"non-medicinal treatment/concomitant therapy for colitis ulcerative
Presence/absence of	(including surgery)" and when any concomitant therapy considered
concomitant therapy	as surgery is included in "[Humira UC] Conversion data provided for
(surgery)	analysis".
	When the data applicable to surgery are contained, regard it as "with
	surgery". Others are "without surgery".
	If "leukocytapheresis" in "non-medicinal treatment/concomitant
Presence/absence of	therapy (including surgery) for colitis ulcerative" is checked and it is
concomitant therapy	not applicable to with concomitant therapy (surgery) in the survey
(leukocytapheresis)	form, it shall be classified into "with leukocytapheresis". Other cases
	are "no leukocytapheresis".
	If "enteral nutrition therapy" in "non-medicinal
Presence/absence of	treatment/concomitant therapy (including surgery) for colitis
concomitant therapy	ulcerative" is checked and it is not applicable to with concomitant
(enteral nutrition	therapy (surgery) in the survey form, it shall be classified into "with
therapy)	enteral nutrition therapy". Other cases are "no enteral nutrition
	therapy".
	If "intravenous nutrition therapy" in "non-medicinal
Presence/absence of	treatment/concomitant therapy (including surgery) for colitis
concomitant therapy	ulcerative" is checked and it is not applicable to with concomitant
(intravenous nutrition	therapy (surgery) in the survey form, it shall be classified into "with
therapy)	intravenous nutrition therapy". Other cases are "no intravenous
	nutrition therapy".
Presence/absence of	If "other therapy" in "non-medicinal treatment/concomitant therapy
concomitant therapy	(including surgery) for colitis ulcerative" is checked and it is not
(other therapy)	applicable to with concomitant therapy (surgery) in the survey form,
(other therapy)	it shall be classified into "with other therapy". Other cases are "no

Data name	Derivation and calculation methods
	other therapy".

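### As worded, the surgery flags need both a ticked box and a conversion-file entry, so a patient identified by one source alone is coded without surgery; the surrounding text suggests that either source was meant to suffice

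*SAP*

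**What the plan says.** In SAP 10.1 General, the row for prior treatment (surgery) selects surgery if the surgery box "is checked and if any prior treatment considered as surgery" "is included in '[Humira UC] Conversion data provided for analysis". The next sentence assigns the category: "When the data applicable to surgery are contained, regard it as" with surgery. The row closes with a catch-all and has no unknown category: "surgery'. Others are 'without surgery".

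The row for concomitant therapy (surgery) has the same structure. The tick-box condition is joined to the file condition by a further conjunction: "including surgery)' and when any concomitant therapy considered" as surgery is in the conversion file.

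The rows for leukocytapheresis, enteral nutrition, intravenous nutrition and other therapy depend on this flag. Each assigns its own category only where its box "ulcerative' is checked and it is not applicable to with prior" treatment (surgery), and the concomitant rows follow the same pattern.

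The same conversion file is used elsewhere in 10.1. It supplies doses that were entered as other: "If 'Others' of a Humira dose is checked, the dose should be" taken from the file. It also supplies dosing frequencies entered as other and is used to recode reasons for discontinuation.

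**The concern.** A programmer who follows the first sentence will code a logical AND. A patient whose form has surgery ticked but who has no entry in the file, or who has an entry in the file but no tick, then goes into the without-surgery group.

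The output would not reveal this. SAP 9.2 and 9.5 keep unknown and not-provided patients out of the tests, but these patients would not be in such a category. They would sit in the comparison group.

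Both surgery flags are background factors tested in Tables 2.9 and 3.4, and in Table 3.4.1, which uses the same list. These tables serve the third survey objective in SAP 4.1, factors that may affect safety and effectiveness. A factor that is significant in Table 2.9 also leads to a further breakdown in Table 2.9.xx. A second programmer who reads the row in its context could code OR and obtain different tables from the same data.

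**Working it through.** The plan states no figure to reproduce. The check is a truth table, followed by a comparison with the neighbouring rows.

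**1. Truth table.** Let A = surgery box checked and B = therapy classed as surgery in the conversion file.

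| A | B | Coded under A AND B | Coded under A OR B |
|---|---|---|---|
| yes | yes | with | with |
| yes | no | without | with |
| no | yes | without | with |
| no | no | without | without |

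The two readings differ in exactly the two single-source cells.

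**2. Wording of other two-source rules in 10.1.** Most prior-medication rows join drug code and tick box with an explicit alternative; the corticosteroid row has "or if corticosteroids in the survey form is checked". Two rows, prior medication (others) and prior medication (other biological products), join tick box and drug-code data with a conjunction. The section therefore uses both connectives, and a programmer has reason to take the difference as deliberate.

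**3. Context of the surgery rows.** The assigning sentence does not repeat a both-sources condition. The four neighbouring rows in each set exclude what counts as surgery. That makes most sense if an entry ticked under another therapy can become surgery through the conversion file, which is the no/yes line of the table. Under AND that line stays without surgery, and the entry remains in the other therapy's category.

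**4. Size.** Let a = patients ticked, b = patients classed as surgery in the file, k = patients in both.

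- AND gives k with surgery; OR gives a + b − k.
- Share lost under AND = (a + b − 2k) / (a + b − k).

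The documents give none of a, b or k. The counts below are assumed, only to show how far the answer moves:

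- a = 40, b = 10, k = 0: AND 0, OR 50; loss 50/50 = 100%.
- a = 40, b = 10, k = 10: AND 10, OR 40; loss 30/40 = 75%.
- a = 40, b = 50, k = 40 (file holds all surgery entries): AND 40, OR 50; loss 10/50 = 20%.
- a = b = k: no loss.

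The possible range is 0 to 100%, so no estimate can be given.

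**5. Reach.** The Table 2.9 factor list has 57 entries by count. Two are the surgery flags. Six more (leukocytapheresis, enteral nutrition and intravenous nutrition, each prior and concomitant) are defined by excluding surgery, so 2 + 6 = 8 of 57 could change. The two other-therapy flags are not in that list; they belong to the classification that Table 1.12 uses. The overall prior-treatment and concomitant-therapy flags do not use the surgery rule.

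**The case against.** The strongest reply is that the rows do not really say AND. A repeated if, or if followed by when, can list two sources that each count, and the assigning sentence then needs only that surgery data be present. On that reading the SAP already describes a union, and the issue is one of wording. This stands in part: either source sufficing is the more likely intent. It does not cure the rule, because the assigning sentence never says which data qualify, and the sentence that does say so is conjunctive.

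A second reply is that the content of the conversion file is inferred. That is correct. Its use for doses, frequencies and discontinuation reasons suggests that it holds recoded other entries, but the surgery rows do not say so. The file could equally hold coded versions of ticked entries.

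A third is that the neighbouring exclusions also have an effect under AND, for example when surgery and another therapy are both ticked and the file has an entry. This also stands. The exclusions favour a union but do not prove one.

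A reader might go further and infer that most patients with recorded surgery will be lost and the with-surgery group will almost vanish. The documents do not support that. It would follow only if the file holds nothing but recoded entries, and no counts are given. Nor does either document call surgery a marker of the most severe disease, so the point cannot rest on that.

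**Conclusion.** The point holds as a conflict between a literal rule and its context. Read literally, both surgery rows require both sources and place single-source patients in the without-surgery group, while the assigning sentence and the neighbouring rows suggest that one source was meant to be enough. That the connective is conjunctive and the remainder is without surgery rests on the text alone. That a union was intended is an inference, though the better supported one.

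The size is unknown. The consequence is limited to the surgery rows of Table 1.12, the surgery factors in the exploratory Tables 2.9, 3.4 and 3.4.1 (with 2.9.xx if a factor is significant), and the therapy flags that depend on the surgery flag. No overall adverse-reaction incidence or remission rate uses these flags. The correction is still worth making, because any misclassification would not be visible in the tables.

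**What to change.** In SAP 10.1, in both the prior-treatment (surgery) and concomitant-therapy (surgery) rows, define surgery as: surgery box checked, OR an entry classed as surgery in the conversion file. State also that the leukocytapheresis, nutrition and other-therapy rows use the flag so defined.

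If the file is instead meant to confirm ticked entries, say so, and add an OR branch for entries recoded to surgery from another therapy box.

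The cost is a change of connective in two rows and, if the program used AND, a re-run of the affected rows and factors. No new data are needed. Reporting the counts for ticked only, file only and both would show whether the choice made any difference.

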- 9) Other concomitant drugs: drug name, reason for use, administration route, dose, and administration period
- 10) Drugs/combination therapies other than medication for ulcerative colitis

Presence or absence of drugs/combination therapies other than medication for ulcerative colitis, name of therapy, and therapeutic duration

11) Presence or absence of onset of tuberculosis or serious respiratory disorders

Examination day, imaging diagnostic method, abnormal findings, and abnormality

12) Mayo Score

Examination day (at initiation of administration, week 4, 8, 16, 24, 32, and 52 of administration, and discontinuation of administration)

13) CRP

Examination day (at initiation of administration, week 4, 8, 16, 24, 32, and 52 of administration, and discontinuation of administration)

14) Endoscopic finding

Examination day (at initiation of administration, week 24, 52 of administration, and discontinuation of administration)

15) Overall improvement (judgment by attending physician)

Judgment day (at week 52 of administration or at discontinuation)

Overall improvement (Remarkably effective, Effective, Ineffective, and Unevaluable)

16) Adverse events (including abnormal change in laboratory values)

Occurrence of adverse events, name of adverse events, onset day, seriousness, causal relationship to this drug, suspected drug(s), symptom and clinical course, treatment (with this drug or symptomatic treatment), outcome, laboratory values (if abnormally changed), and judgment reason if no causality

17) Key survey items

Infection, tuberculosis, malignant tumor, administration site reaction, autoimmune disease, pancytopenia, demyelinating disorders, congestive cardiac failure, and interstitial pneumonia

18) Measurement of anti-adalimumab antibody

If measurement of anti-adalimumab antibody is judged to be necessary

9. Analysis and Methods

- (1) Analytical items
 - 1) Patient population
 - 1. No. of enrolled patients
 - 2. No. of CRFs recovered
 - 3. Safety evaluation set
 - 4. Efficacy evaluation set
 - 2) Safety
 - 1. List of adverse reactions and infections
 - 2. Factors likely to affect the safety

- Incidence of adverse reactions by patient background
- Presence or absence of the use experience with anti-TNFα preparation and the relationship of safety.
- Safety in Long-Term administration
- Relationship of safety when anti-adalimumab antibody was determined
- Safety in patients conducting self-administration

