	concomitant medication.
	When concomitant-medication data are contained in the survey form,
	it should be classified as "with concomitant medications". When
	there is no description of "presence/absence of prior/concomitant
Presence/absence of	medications" in the survey form or the assessment is impossible, it
concomitant medication	should be classified as "unknown/not provided", and other cases are
	"without concomitant medications".
	◆ Data with drug names in "the administration status of
	prior/concomitant medications for colitis ulcerative", "the
	administration status of other concomitant medication" of the survey
	form.

Data name	Derivation and calculation methods
Data name	 Derivation and calculation methods When the year and month are described for the first administration date of the concomitant medication, impute "1" for the "date". When the year is described for the first administration date of the concomitant medication, impute "1" each for the "month" and "date". When the year and month are described for the final administration date of the concomitant medication, impute the month's final date for the date. When the year is described for the final administration date of the concomitant medication, impute "12" for the month and "31" for the date. When the final administration of concomitant medication < the first administration date of Humira, and/or when the final administration date of Humira < the first administration date of concomitant medication. If the above imputing methods do not help add the date (the first administration date or the final administration date is not provided, etc.), or if the first administration date of concomitant medication are reversed, it should be regarded as a
	 Data with drug names in "priortreatment history for colitis ulcerative" of the survey form When the year and month are described for the first administration date of the prior medication, impute "1" for the "date". When the year is described for the final administration date of the prior medication, impute "1" each for the month and the date. If the final administration date of the prior medication ≥ the first administration date of Humira, regard it as a concomitant medication. If the above imputing methods do not help add the date, the final administration date of the prior medication shall be unknown and the case should not be regarded as a concomitant medication.

Data name	Derivation and calculation methods

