	◆ Data with a drug name in "administration status of
	anti-tuberculosis drug" of the survey form
	When the year and month are described for the first
	administration date of anti-tuberculosis drug, impute "1" for the "date".
	When the year is described for the first administration date of
	anti-tuberculosis drug, impute "1" each for the "month" and "date".
	When the year and month are described for the final
	administration date of anti-tuberculosis drug, impute the
	month's final date for the date.
	When the year is described for the final administration date of
	anti-tuberculosis drug, impute "12" for the month and "31" for the date.
	When the final administration of anti-tuberculosis drug < the
	first administration date of Humira, and/or when the final
	administration date of Humira < the first administration date of
	anti-tuberculosis drug, exclude the case from the calculation for
	concomitant medication. If the above imputing methods do not
	help add the date (the first administration date or the final
	administration date is not provided, etc.), or if the first
	administration date and the final administration date of
	anti-tuberculosis drug are reversed, it should be regarded as a concomitant medication.
	concomitant medication.
	('Clear' refers to a condition where no ambiguous expressions
	like "around", "in the middle", etc. are included and a number
	of figure only is provided.)
Presence/absence of	Refer to "171218 drug list_UC". If concomitant-medication data of
concomitant medication	the applicable drug code are provided in the survey form, regard the
(aminosalicylic acid	case as "with aminosalicylic acid". Others are "without
drug)	aminosalicylic acid".
Presence/absence of	Refer to "171218 drug list_UC". If concomitant-medication data of
concomitant medication	the applicable drug code are provided in the survey form, regard the
(corticosteroids)	case as "with corticosteroids". Others are "without corticosteroids".
Presence/absence of	Refer to "171218 drug list_UC". If concomitant-medication data of

Data name	Derivation and calculation methods
concomitant medication	the applicable drug code are provided in the survey form, regard the
(azathioprine)	case as "with azathioprine". Others are "without azathioprine".

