Detailed classification of "with" biological products	Infliximab, other biological products Reason for discontinuation: lack of effectiveness Reason for discontinuation: adverse events Reason for discontinuation: others Reason for discontinuation: unknown/not provided
Concomitant medications for colitis ulcerative Details classification of	Without the history, with the history, unknown/not provided
Details classification of	Aminosalicylic acid products, corticosteroid, azathioprine &

Data	How to stratify
concomitant	6-mercaptopurine, tacrolimus & ciclosporin, antibiotics, others
medications for colitis	
ulcerative	
Concomitant therapy	Without the history, with the history, unknown/not provided
for colitis ulcerative	without the history, with the history, unknown/hot provided
Details classification of	Leukocytapheresis, surgery, enteral nutrition therapy, intravenous
concomitant therapy for	nutrition therapy, others
colitis ulcerative	nutrition dicrapy, outers
Site of disease	Rectum, colon, unknown/not provided
Details classification of	
a site of disease	Sigmoid, descending, transverse, ascending
"colon"	
Site of disease by type	Rectal only (no colon), including any of transverse or ascending site,
Site of disease by type	others, unknown/not provided
Self administration	Without the history, with the history, unknown/not provided
Self-administration	Without the history, with the history, unknown/not provided
error	without the history, with the history, unknown/hot provided
General improvement	Effective or better, ineffective
rate	Effective of better, memective
Detailed classification	
of effective or better of	Markedly effective, effective
general improvement	iviairodiy ciicciive, ciicciive
rate	
Partial Mayo score	\geq 0 and \leq 3, \geq 3 and \leq 6, \geq 6 and \leq 9, unknown/not provided
CRP	$<0.3 mg/dL, \ge 0.3 mg/dL$ and $<1 mg/dL, \ge 1 mg/dL$, unknown/not provided
Endoscopy results	normal or remission mucosa, mild, moderate, severe

12. Handling of data for test/assessment periods

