Sex, pregnancy/nursing, race, age (year), body weight (kg), BMI (kg/m²), duration of illness (year), indication (registration form), allergy history, smoking history, detailed classification of smoking history, tuberculosis test, hepatitis B test, complication, detailed classification of complications, complication/others, medical history, detailed classification of medical history, prior medication for colitis ulcerative, detailed classification of prior medication for colitis ulcerative, treatment for colitis ulcerative, detailed classification of medical product, concomitant medication for colitis ulcerative, detailed classification of "with" biological product, concomitant medication for colitis ulcerative, detailed classification of concomitant medication for colitis ulcerative, concomitant treatment for colitis ulcerative, detailed classification of the disease site "colon", site of disease by type, partial Mayo score, CRP

Note: For the discontinuation reasons for the detailed classification of pregnant/nursing or 'using' biological products", calculate the percentage to the aggregation item right above the item. For other items, calculate the percentage to the number of target patients.

Overlapped aggregation may occur in the detailed classification of complications and complication of other classification, detailed classification of medical history, detailed classification of prior medications for colitis ulcerative, detailed classification of prior treatment for colitis ulcerative, detailed classification of 'using' biological products', detailed classification of concomitant medications for colitis ulcerative, detailed classification of concomitant treatment for colitis ulcerative, and the detailed classification of site of disease for colitis ulcerative and the site of

disease "colon".

"1.13 Incidence of self-administration error"

Patients for analysis: patients in the safety analysis group

Analysis objective: to show the distribution status for presence/absence of self-administration and the detailed classification of self-administration.

Analysis item: calculate the number of patients in the analysis groups.

Calculate the number of patients per "self-administration" defined in "11. How to stratify data" and the percentage to the number of patients in the analysis groups.

In addition, calculate the number of patients per "self-administration error" and the percentage to the patients 'with' self-administration.

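### Section 11 and Table 1.12 report concomitant medication for ulcerative colitis, but the only SAP derivation counts any concomitant drug, including non-UC and anti-tuberculosis drugs

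*SAP*

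**What the plan says.** SAP 10.1 (General) has one row for presence or absence of concomitant medication. Its rule is unconditional: "When concomitant-medication data are contained in the survey form", the patient is classed as 'with'. A record needs a drug code and must not lie wholly outside the Humira treatment period. Reason for use plays no part. The row names four sources:

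- the survey-form field for "prior/concomitant medications for colitis ulcerative";
- the field "administration status of other concomitant medication' of the survey" form;
- drugs in the UC prior-treatment history whose last date falls on or after the first Humira dose;
- the administration status of "anti-tuberculosis drug' of the survey form". If the start and end dates of "anti-tuberculosis drug are reversed, it should be regarded as a concomitant medication", so such a record still counts.

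SAP Section 11 defines a with/without stratum named "Concomitant medications for colitis ulcerative". The item list of Table 1.12 (SAP 13.1) includes "concomitant medication for colitis ulcerative, detailed classification of concomitant medication for colitis ulcerative". Neither place gives a derivation, and SAP 10.1 and its table of contents list no UC-only variable.

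The factor lists of Table 2.9 and Table 3.4 (reused by 3.4.1) name the item simply as concomitant medication, without a UC qualifier.

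Protocol Section 8(3) collects anti-tuberculosis drugs, UC concomitant drugs and other drugs as separate CRF items. The last is described as "Other concomitant drugs: drug name, reason for use, administration route, dose, and administration period".

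**The concern.** The row label and the only rule that can produce the row describe different things. A programmer following SAP 10.1 would fill the UC row of Table 1.12 with an all-drug flag. A reader would then take the percentage as the share of patients who received UC treatment alongside Humira, when it is the share who received any coded drug. The error runs in one direction: the 'with' share can only be too high.

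The table describes the treated population in a document that supports the regulatory report and the re-examination application (SAP 3.1). There is a second, conditional issue. Factors that may affect safety and effectiveness are a survey objective (SAP 4.1), and an item called concomitant medication is tested in Tables 2.9, 3.4 and 3.4.1. The SAP does not say whether this is the pooled flag or the UC stratum of Section 11.

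**Working it through.** The plan gives no figure for this variable, so there is none to reproduce. The check is a tracing of the variable, followed by an illustration of size.

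**1. Sibling variables, side by side (SAP 10.1)**

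| Variable | Source field | UC only? |
|---|---|---|
| Prior medication | UC prior-medication history | Yes |
| Prior treatment | UC prior treatment, including surgery | Yes |
| Concomitant therapy | UC non-drug or concomitant therapy, including surgery | Yes |
| Concomitant medication | UC field, other-drug field, continuing UC prior drugs, anti-tuberculosis field | No |

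Section 11 labels all four strata as being for UC. Three derivations match that label and one does not. The names of the first three also omit UC in SAP 10.1, so the short name of the fourth does not show that an all-drug row was intended for Section 11.

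**2. Following one record**

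Take a patient whose only coded drug during Humira treatment is an anti-tuberculosis drug. The fourth source applies, so the patient is 'with concomitant medications'. No other derivation exists for the UC stratum, so Table 1.12 shows the patient as 'with' concomitant medication for UC. A patient whose only record is in the other-drug field is classed the same way.

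**3. Size (assumed rates)**

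Let N = 1500 (the target sample size), a = share with no concomitant UC drug, and q = share of those patients who take a non-UC or anti-tuberculosis drug. The documents give neither a nor q.

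Patients wrongly shown as 'with' = N × a × q.

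- a = 0.05, q = 0.3: 1500 × 0.05 × 0.3 = 22.5, about 23
- a = 0.10, q = 0.3, 0.5, 0.7: 45, 75, 105
- a = 0.20, q = 0.7: 1500 × 0.20 × 0.7 = 210

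The reported 'with' share is (1 − a) + a × q. At the low end it moves from 95% to 0.95 + 0.015 = 96.5%. At the high end it moves from 80% to 0.80 + 0.14 = 94%. If q = 0 there is no error.

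**4. Factor tests, only if the label means the UC stratum**

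Suppose a = 0.10 and q = 0.5, with adverse-reaction rates of 25% with and 15% without a UC drug, and the misplaced patients having the 15% rate. The 'without' group falls from 150 to 75. The 10-point difference is multiplied by 0.90 / 0.95 = 0.947 and becomes 9.5 points. Approximate power falls from 0.81 to 0.46. Every input here is assumed. If the label means any drug, none of this applies.

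**The case against.** The strongest reply is that the link is inferred. Neither Section 11 nor Table 1.12 says that the UC stratum uses the pooled row, and the SAP does distinguish UC drugs elsewhere: Table 2.3 item 18 ranks them ahead of others. The item list of Table 1.12 is also visibly disordered, naming UC concomitant medication twice. This is fair as far as it goes. But the Section 11 label is clear on its own, and no second derivation exists. Either the pooled row is used, and the figure is wrong for its label, or the row has no definition. Both need the same repair.

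Three stronger readings are tempting and are not supported.

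- *The factor tests in Tables 2.9, 3.4 and 3.4.1 are wrong.* A reader might infer this because the neighbouring items in those lists shorten UC-only variables in the same way. But the printed label is just concomitant medication, which the all-drug flag fits. The SAP does not say that it means the UC stratum.
- *The 'others' and 'antibiotics' classes are contaminated by non-UC drugs.* The class rules refer to a UC drug list (171218) that is not in the documents, so this cannot be checked. Neither class is a tested concomitant-medication factor. The with/without row does not cite that list, so the list does not rescue it.
- *The 'without' group becomes a healthier one.* Nothing in the documents supports this.

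One further objection stands. In a safety analysis, exposure to a corticosteroid or immunosuppressant can matter whatever the reason for use. Limiting the drug-class factors of Table 2.9 to the UC field would be a debatable trade-off, and it is not asked for here.

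**Conclusion.** The point holds for one descriptive row. SAP 10.1 offers only an all-drug flag for a row that Section 11 and Table 1.12 call UC-specific. Followed as written, it counts patients with no concomitant UC drug as having one. The UC-only sources of the three sibling variables suggest an oversight rather than a choice.

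The number affected cannot be found from the documents. The range of 23 to 210 of 1500 (1.5% to 14%) rests on the assumed 5–20% without a UC drug and 30–70% of those on another drug. Any effect on the factor tests depends on a reading that the SAP does not state. What is established for those tables is an ambiguity about which variable is meant. The sample size is unaffected. Severity: minor.

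**What to change.** 1. Add a derivation to SAP 10.1 for concomitant medication for UC. Limit it to the UC concomitant-drug field plus UC prior drugs still running at the first Humira dose, with the existing date rules. Use it for the with/without stratum in Section 11 and the matching row of Table 1.12.
2. Keep the pooled flag under a distinct name, such as 'any concomitant medication', for uses such as Table 2.3 item 18.
3. State which of the two is the overall concomitant-medication factor in Tables 2.9, 3.4 and 3.4.1. The drug-class factors in safety Table 2.9 can stay on the all-drug pool.

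If the sponsor does want an all-drug row in Table 1.12, the minimum is to remove the UC qualifier from the Section 11 stratum and the table.

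The cost is a few lines of SAP text and one source filter in the programs. The CRF already keeps the fields apart, so no new data are needed.
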